## 2. Follow-up Blood Sampling and Ongoing Contact with Medical Monitor

After the initial investigation, regardless of results, serum chemistry is to be performed (using the central lab retest kit) per the schedule below (Table 3) and close contact with the medical monitor with a minimal contact frequency (as outlined in the table) is also expected.

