## 4. Discontinuation of Study Treatment:

For subjects during the first 3 months of treatment with study drug, treatment must be discontinued if any of the following occurs:

- ALT or AST  $> 5 \times \text{ULN}$
- ALT or AST  $> 3 \times \text{ULN}$  and total bilirubin  $> 2 \times \text{ULN}$  or INR  $> 1.5$
- ALT or AST  $> 3 \times \text{ULN}$  with the appearance of fatigue, nausea, vomiting, right upper quadrant pain or tenderness, fever, rash, and/or eosinophilia  $> 5\%$

For subjects that have completed 3 months of treatment with study drug, treatment must be discontinued if any of the following occurs:

- ALT or AST  $> 8 \times \text{ULN}$

- ALT or AST  $> 5 \times \text{ULN}$  for more than 2 weeks
- ALT or AST  $> 3 \times \text{ULN}$  and total bilirubin  $> 2 \times \text{ULN}$  or INR  $> 1.5$
- ALT or AST  $> 3 \times \text{ULN}$  with the appearance of fatigue, nausea, vomiting, right upper quadrant pain or tenderness, fever, rash, and/or eosinophilia  $> 5\%$

5. SAE Reporting

Subjects who meet the criteria for discontinuation of study treatment should have the event reported as an SAE and should follow the SAE reporting process, as outlined in Section 12.3.2 of the protocol.

6. Continuation or Resumption of Study Treatment:

Study treatment may continue in asymptomatic subjects who do not meet the discontinuation rules, however, the investigator/site must adhere to the blood sampling and contact with Medical Monitor schedule in Table 3.

For subjects resuming treatment after an interruption of less than 7 days, the blood sampling schedule in Table 3 should be followed. In case treatment is resumed after interruption of more than 7 days, resumption of treatment must be discussed with and approved by the sponsor medical monitor. In these cases, follow-up blood sampling should occur weekly for the first month and thereafter Table 3 should be followed. Dosages should be at the same level as before the interruption.

7. Characterization of T-cell Response in Subjects Previously Treated with atabecestat

Additional blood draws of 120 mL may be taken from subjects with elevated hepatic enzymes for PBMCs to be isolated and used in an optional immunologic sub study (see Attachment 4).

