1. INTRODUCTION

This statistical analysis plan (SAP) contains definitions of analysis populations, derived variables and statistical methods for the analysis of efficacy and safety for study 54861911ALZ2003.

Screening, randomization, and dosing in this study was stopped on 17 May 2018. Randomized subjects were to continue in the double-blind treatment phase without treatment (as allowed by protocol) for approximately 3 to 6 months from cessation of dosing. This permitted continued safety monitoring of the subjects per protocol. The planned last-patient-out date is 17 September 2018, except for some subjects who may require further follow-up.

At the time of cessation of screening and randomization, 557 (34%) subjects of the planned 1650 had been randomized. The planned duration of treatment was 54 months. As of the time of cessation of dosing, no subject had more than 27 months of treatment and 447 had 12 months of treatment or less.

As a result of the significantly reduced sample size, the objectives of the study as stated in the protocol and in Section 1.1 below cannot be evaluated. Safety outcomes will be summarized with descriptive statistics. The planned interim analysis of CSF A β ₁₋₄₀ was performed but other planned interim analyses will not be performed. Between-group comparisons of selected efficacy outcomes will be performed. Other efficacy outcomes will be summarized with descriptive statistics

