2.4. Visit Windows

As subjects do not always adhere to the protocol visit schedule, the following rules are applied to assign actual visits to analysis visits. Listed below are the visit windows and the target days for each visit. The same definitions will apply to visits before or after the treatment end date using the Analysis Day as defined in Section 2.3 above. The time period description will be appended with '(On-Trt)' for post-baseline visits on or prior to the treatment end date. The time period description will be appended with '(Off-Trt)' for post-baseline visits after the treatment end date. If a subject has 2 or more actual visits in one visit window, the visit closest to the target day will be used as the protocol visit for that visit window. The other additional visit(s) will not be used in the summaries or analyses but they can be used for determination of clinically important endpoints. If 2 actual visits are equidistant from the target day within a visit window, the later visit will be used.

All assignments will be made in chronological order. Once a visit date is assigned to a visit window, it will no longer be used for a later time point except for the endpoint. Listed below (Table 1) are the visit windows and the target days for each visit defined in the protocol.

Table 1: Visit Windows for on and off-treatment Analysis

Scheduled Visit Number	Time period (label on output)	Time Interval (Day*)	Target Time Point (Day)
7	Baseline	-120 to 1	1
8	Week 2	2 to 22	15
9	Week 4	23 to 36	29
10	Week 6	37 to 50	43
11	Week 8	51 to 64	57
12	Week 10	65 to 81	71
13	Month 3	82 to 106	92
14	Month 4	107 to 134	120
15	Month 5	135 to 165	148
16	Month 6	166 to 211	183
17	Month 8	212 to 256	239
18	Month 9	257 to 288	274
19	Month 10	289 to 333	302
20	Month 12	334 to 410	365
21	Month 15	411 to 501	456
22	Month 18	502 to 592	547
23	Month 21	593 to 683	638
24	Month 24	684 to 774	729
25	Month 27	775 to 865	820
26	Month 30	866 to 956	911
27	Month 33	957 to 1047	1002
28	Month 36	1048 to 1138	1093
29	Month 39	1139 to 1229	1184
30	Month 42	1230 to 1320	1275
31	Month 45	1321 to 1411	1366
32	Month 48	1412 to 1502	1457
33	Month 51	1503 to 1593	1548
34	Month 54	1594 to 1684	1639
	Month >54	1685 to ∞	1685

* Relative to analysis reference start date if visit date is prior to or on the treatment end date. Relative to treatment end date if visit date is after treatment end date.

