‘End point (On-Trt)’ is defined as the last available post-baseline result among the on-treatment visits. Unscheduled visit results are included in this definition and will be considered as the endpoint value if the unscheduled visit result is the last post-baseline result available among all on-treatment visits. ‘Baseline (Off-Trt)’ will be defined as the same as ‘End point (On-Trt)’. ‘End point (Off-Trt)’ is defined similarly to ‘End point (On-Trt)’ but based on off-treatment visits.

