6.1.1 Liver function tests

Change from the baseline in ALT, AST, alkaline phosphatase, total bilirubin, lymphocytes, and eosinophils will be summarized. Descriptive statistics, shift tables, and percentage of subjects with potentially clinically important values based on change from the baseline will be summarized for these tests as well. Box-Whisker plots will be provided. These summaries and plots will also be presented for the off-treatment period.

The number and percentage of subjects meeting the below liver enzymes criteria during the on-treatment period will be presented by treatment group:

- ALT >8x the upper limit of normal (ULN) or AST >8x ULN.
- ALT >5x ULN or AST >5x ULN.
- Total bilirubin >2x ULN and either ALT >3x ULN or AST >3x ULN.
- Prothrombin International Normalized Ratio (INR) >1.5 and either ALT >3x ULN or AST >3x ULN.

For the off-treatment period, number and percent of subjects with values within normal range at the off-treatment baseline and met the above criteria post baseline will be summarized.

The distribution of the time to first occurrence of an ALT or AST value >ULN while on study medication will be displayed with Kaplan-Meier curves. Subjects who complete or prematurely

discontinue the study medication without an ALT or AST value >ULN will be censored and the end of treatment date will serve as the time of censoring. The distribution of the time to first occurrence of an ALT or AST value >3x ULN will be summarized in the same way. The peak TB (total bilirubin) times the upper limit of the reference range (ULRR) will be plotted against the peak ALT times the upper limit of the reference range (ULRR), on a log10 scale (eDISH plot). These time-to-event plots and eDISH plot will be presented for the off-treatment period as well.

A listing of subjects with clinically important laboratory values will be provided that displays all values over time for subjects with at least one post-baseline clinically important laboratory value.

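### SAP 6.1.1 counts off-treatment liver criteria only in subjects normal at their last on-treatment value, so a criterion first met after stopping by a subject already above normal is in neither table

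*SAP*

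**What the plan says.** SAP 6.1.1 names four criteria and gives two entry rules for counting them.

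- On treatment: the number and percentage of subjects "meeting the below liver enzymes criteria during the on-treatment period will be presented by treatment group". No condition is placed on the starting value.
- Off treatment: subjects "with values within normal range at the off-treatment baseline and met the above criteria post baseline".

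SAP 2.4 supplies the boundary and the baseline. The on-treatment label is used "for post-baseline visits on or prior to the treatment end date"; anything later is off-treatment. End point (On-Trt) "is defined as the last available post-baseline result among the on-treatment visits", unscheduled results included, and Baseline (Off-Trt) is set equal to it.

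The protocol determines who arrives at that baseline with raised enzymes. Attachment 3, item 6: "Study treatment may continue in asymptomatic subjects who do not meet the discontinuation rules". Attachment 3, item 4 requires a stop at ALT or AST >3x ULN "with the appearance of fatigue, nausea, vomiting, right upper quadrant pain or tenderness, fever, rash, and/or eosinophilia", a rule with no matching row in SAP 6.1.1. The SAP Introduction adds: "Screening, randomization, and dosing in this study was stopped on 17 May 2018". That stop applied to everyone, whatever their enzyme level.

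**The concern.** The on-treatment table closes at the last dose, and the off-treatment table opens only to subjects who were normal at that point. A subject who was above normal but had not yet met a given criterion is between the two. If liver injury progresses after the drug is withdrawn, the new event has no row to go into.

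Hepatic enzyme elevation is the reason Protocol Amendment 6 gives for stopping dosing, and subjects were kept in the study for about 3 to 6 months afterwards for safety monitoring. The subjects left out of the off-treatment criteria count are those already showing a liver signal when the drug was withdrawn. The rows affected are the more serious ones: high transaminase multiples, and transaminase elevation combined with raised bilirubin or INR.

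**Working it through.** The plan states no figure on this point and no formula applies. The check is to trace subjects through the two entry rules. The multiples below are illustrative assumptions, not trial data.

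| Case | Last on-treatment state | After last dose | On-treatment table | Off-treatment table |
|---|---|---|---|---|
| A | ALT 2x ULN, never >5x on drug | ALT 6x | Not in >5x row (2x is not >5x) | Not in >5x row (baseline not normal) |
| B | ALT normal | ALT 6x | Not in >5x row | In >5x row |
| C | ALT 6x | ALT 9x | In >5x row, not in >8x row | Not in >8x row (baseline not normal) |
| D | AST between 3x and 5x, bilirubin below 2x | AST still >3x, bilirubin now >2x | Not in bilirubin row | Not in bilirubin row (baseline not normal) |

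Cases A and D appear in no row of either table. Case C appears once, but its progression to >8x is not counted. Only case B is handled as one would expect.

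**Is the route realistic under the protocol?** Yes, in three ways.

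1. Asymptomatic subjects who met no stopping rule could stay on drug with raised values, so some could have been above normal when dosing ended for all.
2. In the first 3 months, ALT or AST >5x ULN required a stop (Protocol 10.2). Such a subject is in the on-treatment >5x row and then resembles case C.
3. Coagulation is a screening-only test in Protocol 9.9.6. The post-baseline INR that the protocol schedules is the Attachment 3 retest, 24 to 72 hours after the abnormal result is received. If the drug was stopped before that sample, the INR is off-treatment in a subject the table excludes. If dosing continued to the retest, it is on-treatment and counted. The documents do not fix the order.

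**Are there samples to count?** Yes. Attachment 3, item 2: "After the initial investigation, regardless of results, serum chemistry is to be performed (using the central lab retest kit) per the schedule below". Its Table 3 asks for two draws a week at 5x ULN or above and one a week from 3x to below 5x. Subjects with raised enzymes are sampled most often, but if they were above normal at the last dose, none of their later draws can enter the off-treatment criteria table.

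**What do the other outputs recover?** Each of the four criteria requires ALT or AST above 3x ULN. Every missed subject therefore passes the >3 ULN cut in SAP Attachment 6, which SAP 6.1 applies off treatment with no normal-baseline condition. On that cut the subject also qualifies for the listing. The off-treatment Kaplan-Meier and eDISH outputs carry no such condition either. Two limits remain:

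- Attachment 6 has one cut of >3 ULN each for ALT, AST and bilirubin. It has no >5x, >8x, combined or INR line.
- The eDISH plot sets peak bilirubin against peak ALT. It can show case A, case C or an ALT-plus-bilirubin event, but not what makes case D an event if ALT stays low, and not an INR event.

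**The case against.** The best defence is that the restriction is deliberate. A table of new onset from normal separates elevations arising after withdrawal from on-drug injury still evolving, and the SAP uses the off-treatment baseline as its reference in many places. That stands, and it is why the existing rows should be kept. It does not explain why the second group has no rows. For suicidal ideation (SAP 6.4.2), the plan counts rises to 4 or more both from any score below 4 and from 0, and repeats both off treatment. The liver table has only the narrow version.

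It is also fair to say that much of the information survives elsewhere: the PCI counts, shift tables, curves, eDISH plot and listing, hepatic adverse events, and SAE reports for cases meeting a stopping rule.

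Three stronger readings are tempting and are not supported.

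- A reader might infer that these subjects vanish from the liver outputs, or that the Kaplan-Meier curves are wrong. The restriction is written only for the criteria table.
- A reader might scale the count in Protocol 1.4 (11 of more than 200 with enzymes >3x ULN) to the 557 randomized and call the result a bound. That count is from March 2017, pools studies and includes placebo, while Amendment 6 later describes elevations as frequent. The shares who stopped while raised and then met a new criterion are not given.
- A reader might infer that the laboratory window should run to last dose plus 7 days, as for adverse events. That would not close the gap, which persists at any time after stopping. It would also set liver outputs at odds with the by-visit summaries. Nor is 7 days a drug-clearance limit: five half-lives are 5 x 14.4 h = 72 h to 5 x 18.5 h = 92.5 h, or 3.0 to 3.9 days.

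**Conclusion.** The point holds for the two criteria tables. A subject above normal at the off-treatment baseline who first meets one of the four criteria after the last dose is counted for that criterion in neither table. This follows directly from SAP 2.4 and 6.1.1. The SAP does not say whether the normal-range condition applies to the analyte concerned or to all liver tests. A raised ALT excludes a subject from an ALT-based criterion either way, and the broader reading excludes more subjects.

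The size is unknown. What is lost is the by-arm count, chiefly for AST-driven and INR cases; the underlying values remain visible. The analyses are descriptive, so no hypothesis test is affected. The change is still worth making, because the under-count falls on the safety signal that ended development and the correction is cheap.

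**What to change.** In SAP 6.1.1, keep the present off-treatment rows, labelled as new onset from normal. Add a second block by treatment group: for each of the four criteria, the number and percentage of subjects not within normal range at the off-treatment baseline who meet the criterion off treatment, having not met it on treatment. The denominator for each row is subjects not normal at that baseline, without that criterion on treatment, who have at least one off-treatment sample. State which analytes the normal-range condition covers.

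The cost is a few lines of SAP text, one derived flag and four table rows. No new data are needed, and the on/off boundary, baselines, by-visit summaries, curves and eDISH plot are unchanged. New-onset and continuing injury stay separate.

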### 4.1. Inclusion Criteria

Each potential subject must satisfy all of the following criteria to be enrolled in the study.

1. Subject must be a man or woman 60 to 85 years of age, inclusive, at time of informed consent. Subjects 60 to 64 years of age must also have 1 of the following 3 conditions:
  - a. A positive family history for dementia (minimum of 1 first degree relative)
  - b. A previously known *APOE*  $\epsilon$ 4 genotype
  - c. A previously known biomarker status demonstrating elevated amyloid accumulation in CSF or PET
2. Subjects must have a global CDR score of 0 at screening.
3. Subjects must be able to read and write and must have adequate hearing and visual acuity to complete the psychometric tests. The legally acceptable representative must also be able to read and write.
4. Subjects must have evidence of elevated amyloid accumulation by means of either:
  - a. Low CSF  $A\beta_{1-42}$  levels at screening
  - b. A positive amyloid PET scan at screening (depending on the site's PET capability)

*Note: The cut-off value for CSF  $A\beta_{1-42}$  will be based on the value established by the central CSF screening laboratory and specified in a separate laboratory manual. Screening amyloid PET scans will be assessed centrally by a qualified reader for inclusion based on predefined criteria as documented in the imaging manual.*
5. Subjects must be otherwise healthy for their age group or medically stable with or without medication on the basis of physical examination, medical history, vital signs, and 12-lead ECG performed at screening or at baseline.
6. Subjects must be otherwise healthy or medically stable on the basis of clinical laboratory tests performed at screening. If the results of the serum chemistry panel, hormones (thyroid tests), hematology, or urinalysis are outside the normal reference ranges, the subject may be included only if the investigator judges the abnormalities or deviations from normal to be not clinically significant, to be appropriate and reasonable for the population under study, and not to be a potential cause of cognitive impairment. For low vitamin B12 and abnormal thyroid hormone tests, enrollment requires written approval from the sponsor's medical monitor.

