- An increase in Suicidal Ideation Score from baseline at any post-baseline, time point in the // on-treatment period (treatment-emergent suicidal ideation compared to baseline).
- An increase in Suicidal Ideation Score from <4 at baseline to ≥ 4 at any post-baseline, time point in the on-treatment period (treatment-emergent serious suicidal ideation compared to baseline).
- An increase in Suicidal Ideation Score from 0 at baseline to ≥ 4 at any post-baseline, time point in the on-treatment period (emergence of serious suicidal ideation compared to baseline).

In these summaries, the denominator is the number of subjects meeting the baseline criterion.

Listings including additional C-SSRS details will be created for subjects with any suicidal ideation or behavior.

The above summaries will be presented for off-treatment time points, using the off-treatment baseline as the reference time point.

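### The Kaplan-Meier curves for first ALT/AST elevation do not limit the risk set to subjects at or below the threshold at the start, so carried-over elevations are plotted as new events, chiefly off treatment

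*SAP*

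**What the plan says.** SAP 6.1.1 defines the first curve by its event: "The distribution of the time to first occurrence of an ALT or AST value >ULN while on study medication will be displayed". Subjects who finish treatment event-free, or who prematurely "discontinue the study medication without an ALT or AST value >ULN will be censored", with the end of treatment as the censoring time. For the higher threshold, "The distribution of the time to first occurrence of an ALT or AST value >3x ULN will be summarized in the same way". The section then adds: "These time-to-event plots and eDISH plot will be presented for the off-treatment period as well". No sentence sets a condition on who is at risk at time zero, and none gives a time origin or censoring date for the off-treatment versions.

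The same section does set such a condition for a different display. The off-treatment table of liver criteria reports the "number and percent of subjects with values within normal range at the off-treatment baseline and met the above criteria post baseline will be summarized". That condition belongs to the listed count criteria and not to the curves. SAP 6.4.2 is equally explicit for the suicidality summaries: "In these summaries, the denominator is the number of subjects meeting the baseline criterion".

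**The concern.** A curve of time to first occurrence is read as a curve of new onset. If subjects already above the threshold stay in the risk set, their next raised value is drawn as an onset, usually near time zero.

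This matters here because hepatic enzyme elevation is why dosing ended (Protocol, Amendment 6 rationale), and follow-up off drug was kept for safety monitoring (Protocol 1.1). The off-treatment curves should separate new injury after withdrawal from on-drug injury that is resolving. As written they mix the two. Most carry-over should fall in the active arms: of the 11 subjects with elevations above 3x ULN reported in Protocol 1.4, 9 were on active drug, 1 was on placebo and 1 was still blinded.

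**Working it through.** The plan states no figure for these curves, so there is nothing to reproduce. The check is a reading of the text, followed by an illustration with assumed rates.

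**Who can be above the threshold at time zero?**

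- *On treatment, >ULN.* Protocol 4.1 sets no numeric ALT or AST limit. With out-of-range chemistry, "the subject may be included only if the investigator judges the abnormalities or deviations from normal to be not clinically significant". Mild elevations can therefore enter.
- *On treatment, >3x ULN.* The text does not bar this numerically, but few subjects should enter that high.
- *Off treatment, both thresholds.* The liver stopping rules in Protocol 10.2 and Attachment 3 are built on ALT or AST above 3x, 5x or 8x ULN, so a subject stopped for such an elevation has already crossed both curve thresholds. SAP 2.4 sets the off-treatment baseline equal to the last on-treatment result. Attachment 3 calls for repeat sampling within 24 to 72 hours, then twice weekly at 5x ULN or more and weekly from 3x to below 5x. The first off-treatment draw can therefore fall within days, when values may well still be raised.

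**Formula.** Let p be the share of an arm above the threshold at the start, q the probability that such a subject is above it again at a later draw, and r the true incidence among the others. Ignoring censoring, the share of subjects with an event as written is (1 − p)r + p[q + (1 − q)r]. With the risk set restricted it is r.

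**On treatment, >ULN.** Assumed: r = 5% placebo and 20% active; the same p in both arms, because randomization should balance entry status.

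| p | q | placebo | active | ratio |
|---|---|---|---|---|
| restricted | – | 5.0% | 20.0% | 4.0 |
| 2% | 0.5 | 6.0% | 20.8% | 3.5 |
| 5% | 0.5 | 7.4% | 22.0% | 3.0 |
| 10% | 0.8 | 12.6% | 26.4% | 2.1 |

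For example, placebo in the last row is 0.90 × 0.05 + 0.10 × (0.8 + 0.2 × 0.05) = 0.126. The effect is dilution of the contrast.

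**Off treatment, >3x ULN.** Arm size is 557/3, about 186 (SAP 1). Assumed: r = 0.5% in every arm; p = 0.5% on placebo and 2%, 5% or 10% on active.

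With q = 1, the upper bound, the share is p + (1 − p)r:

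- placebo: 0.005 + 0.995 × 0.005 = 0.0100, or 1.9 events
- active at 2%: 0.0249, or 4.6 events
- active at 5%: 0.0548, or 10.2 events
- active at 10%: 0.1045, or 19.4 events

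With q = 0.5:

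- placebo: 0.995 × 0.005 + 0.005 × 0.5025 = 0.0075, or 1.4 events
- active at 2%: 0.98 × 0.005 + 0.02 × 0.5025 = 0.0150, or 2.8 events
- active at 10%: 0.90 × 0.005 + 0.10 × 0.5025 = 0.0548, or 10.2 events

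With the risk set restricted, 186 × (1 − p) × 0.005 gives 0.9 events per arm (0.8 at p = 10%). True off-drug onset was set equal in all arms, so the whole excess on active is carry-over.

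**Censoring.** The written censoring time is the end of treatment. Off treatment, that is when follow-up begins, so event-free subjects would have no time at risk.

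**The case against.** The strongest reply is that other displays already separate baseline status from later status. SAP 6.1 and 6.1.1 plan change from baseline and shift tables by visit, box plots, and a listing of all values over time for subjects with clinically important results, with most of these repeated off treatment. This stands: a reader might infer that the curves are the plan's only information on timing, and they are not. They are its only time-to-event displays of enzyme elevation, and the other tables do not correct a curve that is misleading when read alone.

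On entry elevations, Protocol 9.9.6 asks sites to seek a cause for raised hepatic enzymes and to demonstrate normalization, and exclusion criteria 18 and 22 remove significant or active liver disease. This also stands. One might infer that the on-treatment >ULN curve of each arm jumps by 5 to 10 points at Week 2. That would need 5% to 10% of subjects to enter above ULN, which the documents do not report, and every one of them to be raised again at that draw.

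Off treatment, the documents give no count of subjects stopped for liver reasons. The sponsor ended dosing for everyone on 17 May 2018, so that period also contains many subjects stopped for other reasons. It does not follow that every liver-related stopper becomes an event; only those above the threshold at a later off-treatment draw do.

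Finally, SAP 1.3 says no formal hypothesis testing will be done, and no test is attached to these curves. That limits the consequence to interpretation.

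**Conclusion.** The point holds, with different weight by curve. Off treatment it is material and directional at both thresholds: followed literally, SAP 6.1.1 plots resolving on-drug elevations as new off-drug onsets, mainly in the active arms. It also does so beside a count table that applies a baseline condition. On treatment, the >ULN curve is modestly diluted and expected to be balanced across arms, and the >3x ULN curve is little affected. It would be wrong to read all four curves as equally compromised.

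The size cannot be fixed from the documents. The illustration (up to 1.9 against 4.6 to 19.4 off-treatment events, compared with about 0.9 per arm when restricted) rests on assumed carry-over, onset and persistence; halving persistence gives 1.4 against 2.8 to 10.2. The direction rests only on the stopping rules, the definition of the off-treatment baseline, and elevations being commoner on active drug. Type I error, power and the liver-criteria counts do not change.

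**What to change.** In SAP 6.1.1, define the risk set for each curve: subjects with both ALT and AST at or below that curve's threshold (ULN, or 3x ULN) at the relevant baseline. That is the on-treatment baseline for the on-treatment curves and the off-treatment baseline of SAP 2.4 for the others. Report the number excluded per arm beside each curve. For the 3x ULN curve this set is looser than the normal-range condition on the off-treatment counts, so the SAP should not describe the two as the same.

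For the off-treatment curves, also start the clock at the treatment end date, and censor event-free subjects at their last off-treatment laboratory sample. Without this the curves cannot be produced from the text.

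The cost is a few sentences and a subset flag on data already collected. The downside is that a few subjects leave the curves and must be reported separately. Requiring a return below the threshold before an event can count is an alternative that keeps them in.
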